## I Background and Rationale

Retinal surgery was first performed in the 1960-ies when Charles Schepens developed the technique of scleral buckling using indirect ophthalmoscopy. Later on, pars plana vitrectomy was developed by pioneering surgeons such as Robert Machemer and Relja Zivojinovic. The latter surgical technique became widely adopted in the 1980-ies.

During vitrectomy surgery, there is often the need to remove tissue from the neural retina:

- Epiretinal membranes (ERM): newly formed tissue from dedifferentiated retinal pigment epithelial (RPE) cells. These membranes typically are observed in the following diseases:
  - Macular pucker: formation of fibrosis over the macula, most frequently seen after the formation of posterior vitreous detachment.
  - Proliferative vitreoretinopathy (PVR): formation of fibrotic scars mostly in the (mid)periphery of the retina, most frequently seen in long-standing retinal detachment and after previous retinal surgery.
- Inner Limiting Membrane (ILM): the most inner layer of the retina, formed by the basal membranes of the Müller cells. The removal of this ILM is required to treat different diseases of the retina:
  - Macular hole
  - Vitreomacular traction
  - Macular edema
  - Also, in case of surgery for removal of macular pucker or PVR, concomitant removal of the ILM is frequently performed to avoid re-growth of these membranes.

ERM and ILM are both transparent tissues, similar to the neural retina. Hence, it is not that easy to remove ERM and ILM without touching (and damaging) the underlying neural retina. For this purpose, vital dyes have been developed to selectively stain the tissues that need be removed without staining the underlying neural retina.

The first dye used (off-label) to stain the ILM was Indocyanine Green (ICG), but several reports of toxicity after using that dye have been published. Hence, its use is nowadays mostly abandoned.

Shortly thereafter, Trypan Blue (TB) was introduced to stain ERM. Till today, this dye is used on-label and available from different manufacturers. TB is commercialized in a 0.06% concentration to stain the lens capsule and in a 0.15% concentration to stain ERM. Although TB has good staining properties of ERM, it induces only minimal staining of the ILM.

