A few years later, Brilliant Blue G (BBG) was commercialized to selectively stain ILM, and is today still the golden standard for ILM staining. BBG offers a good and selective staining of the ILM, and is a rather transparent solution, hence the surgeon can see the surface of the retina during the surgery. However, BBG hardly stains the ERM.

The first commercial TB and BBG vital dyes were dissolved in BSS, hence had the same gravity as the BSS used to infuse the eye during vitrectomy surgery. As a result, when injecting a 'cloud' of the vital dye, it was difficult for the dye to reach and color specifically the desired retinal tissue. In newer commercial products, the dyes are dissolved in a heavier-than-water dissolvent (such as poly-ethylene glycol: PEG), which makes them sink down to the retinal surface when injected in the vitreous cavity during surgery.

Since it is frequently necessary to remove both ILM and ERM during vitrectomy surgery, solutions that combine TB and BBG are now also available.

In UZLeuven, two types of vital stains are being used during vitrectomy surgery:

- BBG 0,025 % dissolved in PEG (ILM Blue® – DORC): when only ILM peeling is required.
- BBG 0,025 % + TB 0.15% dissolved in PEG (Membrane Blue Dual® – DORC): when either ERM removal is required, or combination of ERM + ILM removal.

More recently, two new staining dyes were commercialized by ARCADOPHTA:

- Monoblue ILM View: DDG 0.025 % dissolved in PBS (phosphate buffer saline) with 2.6% diglycerol. DDG is a triphenylmethane dye with a chemical formula:  $C_{46}H_{46}N_3NaO_7S_2$  and a molecular weight of 840 Dalton. This dye is used to stain the ILM, similar as ILM Blue. The diglycerol makes it heavier than water to optimize the contact between the dye and the retina, similar as ILM Blue.
- Monoblue Dual View: DDG 0.025 % and Trypan Blue 0.09% dissolved in PBS with 2.6% diglycerol, which is used the same way as Membrane Blue Dual.

In laboratory and ex vivo tests, it was shown that both dyes have the following properties:

- Monoblue ILM view:
  - It stains ILM as good as ILM Blue.
  - It is heavier than water, hence sinks down to the retinal surface.

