### 2.2 Primary Endpoints

Efficacy: visualization of membranes stained based on binary subjective evaluation.

Assessment of efficacy (success) is provided in section 3, Study Endpoints. |

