## 3 Study Population / Eligibility Criteria

### 3.1 Inclusion criteria

Participants eligible for inclusion in this Study must meet **all** of the following criteria:

Adult patients who underwent for vitrectomy surgery where ILM and/or ERM removal is required:

- Macular holes (ILM staining)
- Macular pucker (ILM and ERM staining)
- Vitreomacular traction (ILM staining)

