## 4 Statistics and Data Analysis

The primary outcome of the study is the success of the products based on assessment of efficacy of the staining dye.

Safety of the dye will be assessed by comparing the surgical outcome of the patients to a similar control group that underwent surgery using the staining dyes presently used in our department (see study endpoints).

Statistical analyses will be performed with R version 3.6.2 or higher. In case of missing values, the underlying missingness process (MCAR, MAR or MNAR) will be investigated and 15 multiple imputations will be performed using the **MICE** R package.

We will test with the statistical test of Jamshidian and Jalal (2010), implemented in the **MissMech** R Package (Jamshidian, Jalal & Jansen, 2014), whether missing data were MCAR. If they were not MCAR, we investigated whether or not the missing mechanism could be explained by baseline characteristics (eg, sociodemographic, medical features) of patients using logistic regression, which would suggest an MAR mechanism. If missing data were not MCAR or MAR, they were considered as MNAR.

For each dataset created, two propensity scores will be performed: a first one between the Monoblue ILM View and the ILM Blue, and a second one between the Monoblue Dual View and Membrane Blue Dual. The next covariates were selected for the propensity score: age, gender, visual acuity of the affected eye, surgery type of the affected eye (vitrectomy only vs phaco and vitrectomy). The Covariate Balancing Propensity Score provided in the R **CBPS** package (Imai & Ratkovic, 2014) will be used to estimate an Average Treatment Effect (ATE). The ATE will be estimated by covariate balancing and requesting an exact match. An absolute standardized difference less than 10–15% will be considered to support the assumption of balance between the groups. Unlike the P-value, this method is not affected by the sample size, and it could be used to compare the relative balance of variables that were measured in different units (Austin, 2011). Results (obtained after matching) will be expressed as the mean and standard deviation (SD) for continuous variables or the percentage for categorical variables. The **survey** R package will be used to perform linear regressions for continuous outcome variables and logistic regressions for binary variable. These regressions

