**Primary endpoint: Study product efficacy (success, defined as follows):**

From the surgical report, the following data will be extracted:

1. In case of surgery for macular hole or vitreomacular traction:

- A. Was the staining of the ILM satisfactory to initiate the peeling: yes / no
- B. Was the staining of the ILM satisfactory to create the ILM rhexis: yes / no
- C. Was it necessary to use another vital dye in order to obtain satisfactory staining: yes / no

Success is defined as answer “yes” to 1.A and/or 1.B

2. In case of surgery for macular pucker:

- A. Was the staining of the ERM satisfactory for its removal: yes / no
- B. In case the ILM was removed separately from the ERM:
  - i. Was the staining of the ILM satisfactory to initiate the peeling: yes / no
  - ii. Was the staining of the ILM satisfactory to create the ILM rhexis: yes / no
- C. Was MONOBLUE DUAL View repeatedly injected: yes / no
- D. Was it necessary to use another vital dye in order to remove the ERM: yes / no
- E. Was it necessary to use another vital dye in order to remove the ILM: yes / no

Success is defined as “yes” answer to 2.A and 2B.i or 2B.ii

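### The macular pucker success rule requires a yes on ILM items that are asked only when the ILM was removed separately, and gives no rule for the other eyes

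*Combined protocol and SAP*

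**What the plan says.** Section 5.2 of the combined protocol and SAP lists the items to be taken from the surgical report. For macular pucker, 2.A asks whether ERM staining was good enough to remove the membrane. Items 2B.i and 2B.ii ask whether ILM staining was good enough to start the peel and to make the rhexis, but only "In case the ILM was removed separately from the ERM". Every item is yes/no. Success is a yes "answer to 2.A and 2B.i or 2B.ii", without brackets.

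Section 1 shows that eyes without separate ILM removal are foreseen. For pucker or PVR surgery it says that "concomitant removal of the ILM is frequently performed", which is not the same as always. The reference dual dye is used "when either ERM removal is required, or combination of ERM + ILM removal", and Monoblue Dual View is a product "which is used the same way as Membrane Blue Dual". Section 3.1 annotates pucker with both stainings but does not require separate ILM removal.

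No other text settles the rule. Section 2.2 states: "Assessment of efficacy (success) is provided in section 3, Study Endpoints". Section 3 contains only eligibility criteria. For missing values, section 4 says that "15 multiple imputations will be performed using the" MICE package, without distinguishing missing from not applicable.

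**The concern.** This is the primary outcome, and section 2.3 makes it the basis of a non-inferiority hypothesis. A pucker eye in which 2B was never asked can be scored in three ways: failure (the literal rule), imputed (blank taken as missing), or judged on 2.A alone (2B not applicable). The plan does not choose.

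Under the literal rule, the pucker success rate reflects how often the ILM was removed separately as well as how well the dye stained. Section 2.1 takes the controls from three earlier studies with other purposes, so equal shares cannot be assumed. The propensity covariates in section 4 are age, gender, visual acuity and surgery type (vitrectomy with or without phaco). Separate ILM removal is not among them, so the weighting need not remove an imbalance. Because the data are retrospective, an unwritten scoring choice could be made after results are seen, or differently for study and control eyes.

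**Working it through.** The plan states no success rate, sample size or margin, so there is no figure of its own to reproduce. The check has a logical part and an illustration.

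**Logic.** There are ten answer patterns: 2.A yes or no, combined with four patterns for 2B.i/2B.ii or with 2B not asked. The rule has two possible bracketings. The patterns that matter are:

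| 2.A | 2B.i | 2B.ii | 2.A and (2B.i or 2B.ii) | (2.A and 2B.i) or 2B.ii |
|---|---|---|---|---|
| yes | not asked | not asked | failure | failure |
| no | yes | yes | failure | success |
| no | no | yes | failure | success |

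The first row fails under both bracketings, so the main gap does not depend on the brackets. The other two rows show that the second bracketing lets unsatisfactory ERM staining count as success. The two bracketings agree on the remaining seven patterns.

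**Illustration (assumed rates).** Let a = P(2.A yes) = 0.97, b = P(2B.i or 2B.ii yes, given 2.A yes and separate removal) = 0.98, and p = share with separate removal.

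- Literal: p·a·b, which can never exceed p.
- Imputed (if imputation reproduces b): a·b.
- Not applicable: p·a·b + (1 − p)·a.

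At p = 0.80:

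- literal 0.80 × 0.97 × 0.98 = 76.0%
- imputed 0.97 × 0.98 = 95.1%
- not applicable 0.760 + 0.20 × 0.97 = 95.4%

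*Unequal shares, equal staining.* The literal difference is 0.951 × (difference in shares):

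- 90% v 80%: 9.5 points
- 85% v 80%: 4.8 points
- 90% v 70%: 19.0 points

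With 2B not applicable, 90% v 80% gives 0.97 × 0.02 × 0.10, about 0.2 points. The pattern does not depend on these particular rates: with a = b = 0.95 and shares of 70% (study) v 80% (control), the literal difference is −9.0 points, against +0.5 if not applicable.

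*Equal shares, true ERM deficit of 10 points (a = 0.97 v 0.87).* The literal difference is p·b·0.10; the not-applicable difference is (1 − p + p·b)·0.10.

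| p | Literal | Not applicable |
|---|---|---|
| 0.90 | 8.8 | 9.8 |
| 0.80 | 7.8 | 9.8 |
| 0.50 | 4.9 | 9.9 |

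At p = 0.80 the odds ratio is 0.68 (0.682 v 0.760) under the literal rule and 0.28 (0.856 v 0.954) if not applicable.

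*Precision at p = 0.80, assuming 100 eyes per arm and an unweighted Wald interval.*

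- Literal: SE = √(0.682 × 0.318/100 + 0.760 × 0.240/100) = 0.063. Upper 95% limit of the deficit: 7.8 + 12.4 = 20.2 points.
- Not applicable: SE = √(0.856 × 0.144/100 + 0.954 × 0.046/100) = 0.041. Upper limit: 9.8 + 8.0 = 17.8 points.

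The two limits cross at about 480 eyes per arm. On the odds-ratio scale the lower limits are 0.36 (literal) and 0.10 (not applicable).

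*Brackets, separately peeled eyes only.* Assume P(2B.ii yes) = 0.97 and P(2B.i yes, 2B.ii no) = 0.01, independent of 2.A. The same deficit shows as 0.951 v 0.853 (9.8 points) under the first bracketing. Under the second it is (0.97 + 0.01 × 0.97) v (0.97 + 0.01 × 0.87) = 0.980 v 0.979, or 0.1 points.

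**The case against.** The best defence is that a sub-item introduced by a condition ordinarily counts only where the condition holds, so a sensible analyst would score the other eyes on 2.A alone. That is probably the intent. The imputed and not-applicable scorings also differ by only about 0.4 points before rounding (95.06% v 95.45%), so the large figures come from the literal reading and, for the false difference, from an assumed imbalance that no section documents. All this stands as a limit on size. It does not supply the missing rule, and a primary endpoint should not depend on an analyst's inference.

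Three stronger readings are tempting, and the documents do not support them.

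- A reader might infer that the literal rule favours the study product, because it shrinks a true deficit. That holds for the point estimate and, in the illustration, on the odds-ratio scale. On the difference scale the interval widens, and at 100 eyes per arm non-inferiority becomes harder to show. With no true deficit at all, the upper limits are about 11.8 points (literal) and 5.8 (not applicable). The plan mentions both proportions and logistic regression, and states no margin or sample size, so no direction can be claimed.
- A reader might infer that such eyes are common. The remark in section 1 covers PVR as well as pucker, and PVR is not an eligible indication; the description of dual-dye use is general. The conditional wording of 2B shows that these eyes are foreseen, not how many there are.
- A reader might infer that an eye needing a second dye (1.C, 2.D or 2.E) ought to be a failure. The rule for macular hole and vitreomacular traction is explicit, and these items may serve the secondary endpoint on surgical help. That is a design choice, not part of this gap.

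**Conclusion.** The gap is real and should be closed before analysis. As written, a pucker eye with satisfactory ERM staining and no separate ILM removal cannot be a success under either bracketing, and nothing elsewhere in the plan repairs this. Confidence in the wording gap is high. Its effect cannot be sized from the documents: it is nil if every pucker eye had separate ILM removal, and otherwise grows with the share without it and with any imbalance between arms. Under the assumed rates, a 10-point imbalance in shares produces a false difference of nearly the same size. With equal 80% shares, a true deficit of 9.8 points on the not-applicable scoring shows as 7.8. Whether non-inferiority becomes easier or harder to show depends on the effect scale, margin and sample size. The missing brackets are a second, smaller defect in the same sentence. Macular hole and vitreomacular traction eyes are unaffected.

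**What to change.** Before outcomes are examined, and identically for study and control eyes:

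- (a) Define pucker success as 2.A yes and, only if the ILM was removed separately, (2B.i or 2B.ii) yes, with the brackets written out.
- (b) Add a yes/no item for separate ILM removal, taken from the surgical reports, including those of the controls. Section 5.2 has no stand-alone item for this, so a blank 2B cannot otherwise be told from a missing one. Where the answer is no, code 2B as not applicable and exclude those cells from the imputation.
- (c) Report the share of separate ILM removal in each arm.

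The section 2.2 cross-reference should point to section 5.2.

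The cost is a sentence of rule text, one extra extracted item and some recoding, with no new patients or visits. The main limitation is reliance on existing reports, control reports included, to show whether the ILM was removed separately; the documents do not say whether they do.

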**Secondary endpoint: assessment of surgical safety**

The following endpoints will be used to determine surgical safety:

- Occurrence of adverse events during or after the surgery, whereby both treatment groups will be compared to the corresponding control groups (see above). Occurrence of adverse events will be collected over the duration of the study and up to week 6-10 postoperative, and will be assessed cumulatively.
- Visual outcome at the last postoperative visit, i.e. week 6-10 after the surgery

## 6 Ethical and Regulatory Considerations

### 6.1 Ethics Committee (EC) review & reports

Before the start of the Study, this protocol and other related documents will be submitted for review to the EC for Study authorization. The Study shall not commence until such approvals have been obtained and until other relevant essential Study documents, such as duly signed contract agreements, evidence of adequate Study financing etc. are in place.

### 6.2 Protocol / GCP compliance

The Study must be performed in accordance with the protocol, current ICH and ICH-GCP guidelines, and applicable regulatory and country-specific requirements. ICH guidelines are an international ethical and scientific quality standard for designing, conducting, recording, and reporting studies that involve the

participation of human participants. Compliance with this standard provides public assurance that the rights, safety, and well-being of Study participants are protected, consistent with the principles that originated in the most recent version of the Declaration of Helsinki, and that the Study data are credible, reliable and reproducible.

### 6.3 Data protection and participant confidentiality

The Study will be conducted in compliance with the requirements of the EU General Data Protection Regulation 2016/679 (GDPR), and the relevant Belgian laws implementing the GDPR including the Belgian Privacy Act of 30 July 2018 on the protection of privacy in relation to the processing of personal data. Any collection, processing and disclosure of personal data, such as participant health and medical information is subject to compliance with the aforementioned personal data protection laws.

Any personal data shall be treated as confidential at all times including during collection, handling and use or processing, and the personal data (including in any electronic format) shall be stored securely at all times and with all technical and organizational security measures that would be necessary for compliance with EU and national data protection legislation (whichever is more stringent). The Sponsor shall take appropriate measures to ensure the security of all personal data and guard against unauthorized access thereto or disclosure thereof or loss or destruction while in its custody.

## 7 Research Registration, Dissemination of Results and Publication Policy

The Declaration of Helsinki (latest version) and European and Belgian regulations require that every research Study involving human participants be registered in a publicly accessible database before recruitment of the first participant. The CI is responsible for registering the Study.

In addition, the CI will fulfil their ethical obligation to disseminate and make the research results publicly available. As such the CI is accountable for the timeliness, completeness and accuracy of the reports. Researchers, authors, Sponsors, editors and publishers must adhere to accepted guidelines for ethical reporting. Negative and inconclusive, as well as positive results must be published or otherwise made publicly available. Sources of funding, institutional affiliations and conflicts of interest must be declared in publication.

## 8 Joint Commission International (JCI)

In order to ensure the same quality and safety standards in patient care for clinical research as commonly applied by the Sponsor in its regular activities, and in accordance with JCI standards, the Sponsor shall comply with the following obligations: (a) the Sponsor will use trained and qualified employees or contractors to manage and coordinate the Study; (b) the Sponsor will ensure that multi-center Study reporting is reliable and valid, statistically accurate, ethical, and unbiased. (c) the Sponsor will not grant incentives, other than standard compensations and reimbursement of costs, to Study participants or to participating site's staff that would compromise the integrity of the research; (d) the Sponsor is responsible for monitoring and evaluating the quality, safety, and ethics of the Study and will respect the participating site's policies and processes when performing such monitoring and evaluation activities; (e) the Sponsor will protect the privacy and confidentiality of the Study participants in accordance with all applicable laws.

